# **6.3** Dose Modifications for Infusion-Related Reactions

For patients who have allergic or acute infusion reactions to nivolumab therapy, modifications based on grade should be as follows:

Grade	Action
(CTCAE v.4.03)	
Grade 1	
 
Monitor patient until recovery from symptoms (fever, chills, shakes, itching, rash, hypertension or hypotension, or difficulty in breathing during and immediately after administration of nivolumab); infusion rate may be slowed.
 
If the infusion is interrupted, then restart the infusion at 50% of the original infusion rate when symptoms resolve; if no further complications ensue after 30 minutes, the rate may be increased to 100% of the original infusion rate. Monitor patient closely.
 
The following prophylactic premedication is recommended for future infusions: diphenhydramine 1 mg/kg with max 50 mg (or equivalent) and/or acetaminophen (paracetamol) 10-15 mg/kg (max 1000 mg) at least 30 minutes before additional nivolumab administrations, slowing infusion rate as above.
 

Grade 2	
 
Stop infusion, begin an IV infusion of normal saline, and treat the patient with diphenhydramine 1 mg/kg with max 50 mg IV (or equivalent) and/or acetaminophen (paracetamol) 10-15 mg/kg (max 1000 mg); remain at bedside and monitor patient until resolution of symptoms. Corticosteroid or bronchodilator therapy may also be administered as appropriate.
 
If the infusion is interrupted, then restart the infusion at 50% of the original infusion rate when symptoms resolve; if no further complications ensue after 30 minutes, the rate may be increased to 100% of the original infusion rate. Monitor patient closely.
 

	If symptoms recur, then no further nivolumab will be administered
	at that visit. Administer diphenhydramine 1 mg/kg with max 50 mg
	IV (or equivalent), and remain at bedside and monitor the patient
	until resolution of symptoms. The following prophylactic
	premedication is recommended for future infusions:
	diphenhydramine 1 mg/kg with max 50 mg IV (or equivalent) and
	acetaminophen (paracetamol) (10-15 mg/kg, max 1000 mg) should
	be administered at least 30 minutes before additional nivolumab
	administrations. If clinically indicated, corticosteroids
	(recommended dose: 1-2 mg/kg/day methyl-prednisolone IV or
	equivalent) may be used.
Grade 3 or 4	Immediately discontinue infusion of nivolumab.
Grade 3 or 4	
 
Immediately discontinue infusion of nivolumab.
 
Begin an IV infusion of normal saline, and treat the patient as per
 

Grade 3 or 4	
Grade 3 or 4	Begin an IV infusion of normal saline, and treat the patient as per
Grade 3 or 4	Begin an IV infusion of normal saline, and treat the patient as per institutional guidelines for the treatment of anaphylaxis.
Grade 3 or 4	
 
Begin an IV infusion of normal saline, and treat the patient as per institutional guidelines for the treatment of anaphylaxis.
 
Patient should be monitored until the investigator is comfortable that
 

Grade 3 or 4	
 
Begin an IV infusion of normal saline, and treat the patient as per institutional guidelines for the treatment of anaphylaxis.
 
Patient should be monitored until the investigator is comfortable that the symptoms will not recur.
 

Grade 3 or 4	
 
Begin an IV infusion of normal saline, and treat the patient as per institutional guidelines for the treatment of anaphylaxis.
 
Patient should be monitored until the investigator is comfortable that the symptoms will not recur.
 
Nivolumab will be permanently discontinued.
 

Grade 3 or 4	
 
Begin an IV infusion of normal saline, and treat the patient as per institutional guidelines for the treatment of anaphylaxis.
 
Patient should be monitored until the investigator is comfortable that the symptoms will not recur.
 
Nivolumab will be permanently discontinued.
 
Investigators should follow their institutional guidelines for the
 

Grade 3 or 4	
 
Begin an IV infusion of normal saline, and treat the patient as per institutional guidelines for the treatment of anaphylaxis.
 
Patient should be monitored until the investigator is comfortable that the symptoms will not recur.
 
Nivolumab will be permanently discontinued.
 
Investigators should follow their institutional guidelines for the treatment of anaphylaxis. Remain at bedside and monitor patient
 

Grade 3 or 4	
 
Begin an IV infusion of normal saline, and treat the patient as per institutional guidelines for the treatment of anaphylaxis.
 
Patient should be monitored until the investigator is comfortable that the symptoms will not recur.
 
Nivolumab will be permanently discontinued.
 
Investigators should follow their institutional guidelines for the treatment of anaphylaxis. Remain at bedside and monitor patient until recovery from symptoms. In the case of late-occurring
 

Please note that late occurring events including isolated fever and

fatigue may represent the presentation of systemic inflammation.

Please evaluate accordingly.

## 6.4 Dose Modifications for Skin Rash and Oral Lesions

Skin Rash and	Management/Next Dose of Nivolumab
Oral Lesions	
≤ Grade 1	No change in dose*
Grade 2	
 
Continue protocol therapy.*
 
Topical steroids do not require protocol therapydiscontinuation. If prolonged symptoms require systemic corticosteroids, decisions regarding whether protocol therapymay be reinstituted following weaning of immunosuppression must be made in consultation with Study Chair or Co-Chair.
 

Grade 3	
 
Hold* until ≤ Grade 1; if resolves within seven (7) days, then resume at same dose level.
 
Topical steroids do not require protocol therapydiscontinuation. If prolonged symptoms require systemic corticosteroids, decisions regarding whether protocol therapymay be reinstituted following weaning of immunosuppression must be made in consultation with Study Chair or Co-Chair.
 

Grade 4	Discontinue therapy, systemic corticosteroids indicated.

\*Patients with purpuric or bullous lesions must be evaluated for vasculitis, Steven-Johnson syndrome (SJS), toxic epidermal necrolysis (TEN), and autoimmune bullous disease including oral lesions of bullous pemphigus/pemphigoid. Pruritus may occur with or without skin rash and should be treated symptomatically if there is no associated liver or GI toxicity.

Note: Skin rash typically occurs early and may be followed by additional events particularly during steroids tapering.

**Recommended management:** See Skin AE Management Algorithm (Section 6.4.1).

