#### **5.3** Criteria to Resume Treatment

Patients may resume treatment with study drug when the drug-related AE(s) resolve to Grade ≤1 or baseline value, with the following exceptions:

- Patients may resume treatment in the presence of Grade 2 fatigue;
- Patients who have not experienced a Grade 3 drug-related skin AE may resume treatment in the presence of Grade 2 skin toxicity;
- Patients with baseline Grade 1 AST/ALT or total bilirubin who require dose delays for reasons other than a 2-grade shift in AST/ALT or total bilirubin may resume treatment in the presence of Grade 2 AST/ALT or total bilirubin;
- Patients with combined Grade 2 AST/ALT and total bilirubin values meeting discontinuation parameters should have treatment permanently discontinued;
- Drug-related pulmonary toxicity, diarrhea, or colitis, must have resolved to baseline (Grade 1) before treatment is resumed. Patients with persistent Grade 1 pneumonitis after completion of a steroid taper over at least 1 month may be eligible for retreatment following discussion with the Study Chair or Co-Chair;
- Patients with drug-related endocrinopathies adequately controlled with only physiologic hormone replacement may resume treatment following discussion with the Study Chair or Co-Chair.

If the criteria to resume treatment are met, the patient should restart treatment at the next scheduled time point as per protocol. However, if the treatment is delayed past the next scheduled time point as per protocol, this time point should become day one of the subsequent cycle. If treatment is delayed or interrupted for > 6 weeks, the patient must be permanently discontinued from protocol therapy.

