## 6.2 Dose Modifications for Non-Haematological Toxicity

Patients who have any Grade 3 or Grade 4 non-hematological toxicity attributable to the investigational drug with the specific exclusion of the following, will be removed from the study:

- Grade 3 ALT that returns to levels that meet initial eligibility criteria or baseline within seven (7) days and does not require systemic immunosuppression;
- Grade 3 liver enzyme elevation, including AST/GGT that returns to baseline within 7 days and does not require systemic immunosuppression;
- Grade 3 or 4 serum electrolyte or mineral abnormalities responsive to supplementation;
- Grade 3 or 4 amylase or lipase abnormalities that are not associated with diabetes mellitus (DM), associated liver or gall bladder inflammation or clinical manifestations of pancreatitis;
- isolated Grade 4 amylase or lipase abnormalities that are not associated with symptoms or clinical manifestations of pancreatitis and decrease to < Grade 4 within 1 week of onset;
- Grade 3 rash/oral lesions that resolves to Grade  $\leq 1$  within seven (7) days;
- Grade 3 or 4 seizures (multiple seizures despite medical intervention or life-threatening seizures/status epilepticus) that may occur in the context of pseudo-progression;
- fever greater than 40°C of ≤24 hr. duration;
- Grade 3 fatigue that resolves to Grade  $\leq 2$  within 7 days;
- Grade 3 creatinine increase that resolves to Grade  $\leq 1$  or baseline within seven (7) days.

Patients who experience the following non-hematological toxicities attributable to protocol therapy will also be removed from the study:

- Grade 2 fever that does not resolve to Grade  $\leq 1$  within seven (7) days;
- Grade 2 uveitis, eye pain or blurred vision that does not respond to topical therapy and does not improve to Grade 1 prior to next scheduled dose;
- Grade 2 non-hematological toxicity requiring systemic immunosuppressive therapy. This includes, but is not limited to, autoimmunity of the lung, heart, kidney, bowel, CNS, pituitary or eye;
- Grade 2 endocrine toxicity requiring hormone replacement, with the exception of Grade
   2 hypothyroidism, thyroiditis and thyroid dysfunction adequately managed with thyroid hormone replacement;
- Grade 2 adrenal insufficiency;
- Grade 3 colitis or Grade 3 diarrhea attributable to protocol therapy of more the seven (7) days of duration.

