Any non-hematological toxicity requiring greater than seven (7) days delay in therapy will be criteria for removal from the study. Other non-hematological toxicities attributable to the investigational drug will be dose adjusted as outlined below (see *Section 6.3 – 6.12*).

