# 6.4.1 Recommended Skin Adverse Event Management Algorithm

Toxicity	Management	Follow-up
(CTCAE v.4.03)		
Grade 1-2 Rash: Covering ≤ 30% BSA*	
 
Symptomatic therapy (e.g. antihistamines, topical steroids);
 
Continue protocol therapyas per protocol.
 
	
 
If persists >1-2 weeks or recurs:
 
Consider skin biopsy;
 
Hold protocol therapy;
 
Consider 0.5-1.0 mg/kg/day         Methylprednisolone IV or oral         equivalent;
 
Once improving, taper steroids         over at least 1 month;
 
Consider prophylactic antibiotics         for opportunistic infections
 
Then resume nivolumab therapy         per protocol.
 
If worsens:
 
Treat as Grade 3-4.
 

Grade 3-4	Hold or discontinue therapy	If improves to Grade 1:
Rash: Covering	as per protocol'	• Taper steroids over at least 1
> 30% BSA; life	• Consider skin biopsy;	month;
threatening	• Dermatology consult;	Add prophylactic antibiotics for
consequences*^	• 1.0 – 2.0 mg/kg/day	opportunistic infections
	methylprednisolone IV or IV equivalent.	
 
Resume nivolumab therapy as per protocol.
 

Patients on IV steroids may be switched to an equivalent dose of oral corticosteroids (e.g. prednisone) at start of tapering or earlier, once sustained clinical improvement is observed. Lower bioavailability of oral corticosteroids should be considered when switching to the equivalent dose of oral corticosteroids.

'If Stevens-Johnson syndrome (SJS)/ toxic epidermal necrolysis (TEN) is suspected, withhold nivolumab therapy and refer patient for specialized care for assessment and treatment. If SJS or TEN is diagnosed, permanently discontinue nivolumab therapy.

\*Refer o NCI CTCAE v.4.03 for term specific grading criteria.

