## 7.4 Skin Related Toxicity

For skin-related Grade 3 autoimmune toxicity lasting > 7 days or Grade 4 autoimmune toxicity, including severe generalized pruritus or rash, symptomatic treatment will be given, and patients will be removed from protocol therapy. Therapy will be as clinically indicated and may include local skin care, antihistamines, or corticosteroids (which can be local/topical or systemic). The use of topical corticosteroids for grades 1-3 dermatitis will be allowed, and will not require patients to be removed from study. In the case of late-occurring hypersensitivity symptoms (e.g., appearance within one week after treatment of a localized or generalized pruritus), symptomatic treatment may be given (e.g., oral antihistamine, topical steroids for the skin).

A dermatologist should evaluate persistent (lasting greater than seven (7) days) and/or severe rashes or pruritus. Patients should be advised to seek medical evaluation if they notice new-onset rash. Early consultation with a dermatology specialist and a biopsy should be considered if there is uncertainty as to the cause of the rash, or if there is any unusual appearance or clinical feature associated with it. Other drugs that may cause rash should be considered in the differential and, if possible, discontinued. A biopsy should be performed if appropriate and photos should be obtained.

If symptoms or signs of SJS or TEN appear, nivolumab should be withheld and the patient should be referred for specialized care for assessment and treatment. If the patient has confirmed SJS or TEN, permanent discontinuation of nivolumab is mandatory.

Please refer to *Sections 6.4 and 6.4.1* for dose modification and management of the skin toxicities.

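### Attributable Grade 3 rash lasting more than 7 days leads to removal under Sections 6.2 and 7.4, but Sections 6.4 and 6.4.1 leave restart after steroids open

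*Protocol*

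**What the plan says.** **Rules that remove the patient**

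- Section 6.2 removes patients with attributable Grade 3 or 4 non-haematological toxicity unless a listed exclusion applies. The only exclusion for rash begins "Grade 3 rash/oral lesions that resolves to Grade" and requires resolution to Grade 1 or lower within 7 days.
- Section 6.2 adds a limit on delay: "Any non-hematological toxicity requiring greater than seven (7) days delay in therapy will be criteria for removal from the study".
- Section 6.2 also removes for "Grade 2 non-hematological toxicity requiring systemic immunosuppressive therapy".
- Section 7.4 applies "For skin-related Grade 3 autoimmune toxicity lasting > 7 days or Grade 4 autoimmune toxicity, including severe generalized pruritus or rash", and the stated action is removal from protocol therapy. Section 13.2 refers to Section 7 for the adverse events that require removal, so this rule is operative.

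**Rules that leave restart open**

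- Section 6.4, Grade 3 row: hold until Grade 1 or lower, and resume at the same dose if that happens within 7 days. If prolonged symptoms need systemic corticosteroids, the decision whether therapy may be "reinstituted following weaning of immunosuppression must be made in consultation with Study Chair or Co-Chair". The Grade 2 row has the same sentence.
- Section 6.4.1, Grade 3-4 row: methylprednisolone 1 to 2 mg/kg/day; on improvement to Grade 1, a taper of at least 1 month; then the entry "Resume nivolumab therapy as per protocol".
- Section 5.3 permits restart at Grade 1 or lower and sets a longer limit: "If treatment is delayed or interrupted for > 6 weeks, the patient must be permanently discontinued from protocol therapy".
- Section 7.14 allows resumption after a corticosteroid taper for suspected immune-related reactions.
- Section 7.4 itself sends the reader to Sections 6.4 and 6.4.1 "for dose modification and management of the skin toxicities".

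**The concern.** A child with drug-related Grade 3 rash on day 8 of the hold, started on systemic steroids, falls under both sets of rules. One set takes the patient off nivolumab with no discretion. The other treats restart as a live option once steroids are weaned.

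Consulting the Study Chair or Co-Chair does not settle this, because they read the same conflicting text. Approving restart re-exposes a patient after severe skin toxicity in breach of Sections 6.2 and 7.4. Refusing it may withdraw drug unnecessarily, under Section 6.4, from a patient whose eligibility required that no known curative therapy exist. Sites could also handle and record the same event differently, which affects discontinuation data under the safety objective.

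**Working it through.** No sample size, power or error rate is involved. The check sets the rules side by side for one event and then compares their time limits.

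**1. Disposition by rule**

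| Event | 6.2 | 7.4 | 6.4 | 6.4.1 |
|---|---|---|---|---|
| Grade 3, settles to Grade 1 or lower within 7 days | Spared | Not triggered | Resume, same dose | Resume listed |
| Grade 3, beyond 7 days, systemic steroids | Remove | Remove | Restart open, with Chair or Co-Chair | Taper of at least 1 month, resume |
| Grade 2, systemic steroids | Remove | Not addressed | Restart open, with Chair or Co-Chair | Taper of at least 1 month, resume |
| Grade 4 | Remove | Remove | Discontinue | Shares the Grade 3 row, which has a resume entry |

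The second and third rows conflict. In the Grade 2 row, Section 6.4 itself describes the steroid course as immunosuppression, so it meets the Section 6.2 trigger. For Grade 4, Sections 6.2, 6.4 and 7.4 agree on stopping. The defect there is only that Section 6.4.1 merges Grades 3 and 4 and makes only diagnosed SJS or TEN an explicit permanent stop, so its row is ambiguous.

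**2. Taper against the 7-day limit**

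Assumption: 1 month is 28 to 30 days.

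- 28 / 7 = 4.0
- 30 / 7 = 4.3

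The minimum taper is about four times the limit. Section 6.4 places restart after weaning, so the restart step cannot be reached without first meeting the Section 6.2 delay criterion.

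**3. The same taper against the 6-week limit of Section 5.3**

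Assumptions: delay runs from the start of the hold, and the taper starts when Grade 1 is reached. Six weeks is 42 days.

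- 42 − 28 = 14 days left before the taper must start
- 42 − 30 = 12 days left

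A Grade 3 rash that reaches Grade 1 between day 8 and about day 12 to 14 of the hold can complete a minimum taper in time. That patient may restart under Sections 5.3, 6.4 and 6.4.1 and is removed under Sections 6.2 and 7.4.

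**4. Sensitivity to how delay is counted**

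Take the most favourable case: a dose is given, and the rash and taper both start that day. The next dose is due on day 14, or day 16 using the 2-day window.

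- 28 − 14 = 14 days' delay
- 28 − 16 = 12 days' delay

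Both exceed 7 days and both are below 42, so the conflict does not depend on the counting convention.

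**5. How other tables in Section 6 are written**

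The nausea/vomiting and fever tables state that the patient goes off therapy if the time limit is missed. The pancreatitis and endocrine tables refer to the exceptions in Section 6.2. The rash table does neither: its Grade 3 row gives no action for a rash that has not resolved by 7 days, apart from the consultation sentence.

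**The case against.** The strongest counter-argument is an ordering within Section 6.2. After listing what leads to removal, it sends only the remaining attributable toxicities to Sections 6.3 to 6.12. Read in that order, Grade 3 rash beyond 7 days is removed before Section 6.4 is reached, and Section 7.4 agrees. This is a fair reading and probably the intended one, but it does not cure the text. It leaves the reinstitution sentence in Section 6.4 with practically no case to apply to, since systemic steroids for prolonged symptoms followed by weaning do not fit within 7 days' delay. Section 7.4 still directs readers to that sentence, and Sections 5.3 and 7.14 support restart.

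Other points stand in part:

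- Section 6.4 requires consultation and does not instruct restart; the answer could be no. It still presents restart as open where two other sections close it.
- Section 6.4 speaks of prolonged symptoms and does not say more than 7 days. The bullet before it covers resolution within 7 days, so the longer case is the natural meaning.
- Section 6.4.1 is headed as a recommendation and defers to the protocol. That softens Section 6.4.1 but not Section 6.4, which is the dose-modification table.
- The day 8 to 12-14 window depends on the counting rule and can move by up to two weeks.
- The problem is not confined to skin. Section 6.7 resumes after steroid-treated Grade 2 pneumonitis, while Section 6.2 names the lung among its Grade 2 removals.
- The Study Chair or Co-Chair must be notified of dosage modifications, which limits undetected divergence between sites.

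**Conclusion.** The concern holds and should be corrected. Attributable Grade 3 rash lasting more than 7 days has two incompatible dispositions, and Grade 2 rash needing systemic steroids has the same conflict. The Grade 4 issue is an ambiguity in one row of Section 6.4.1.

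The size is a restart path about 4.0 to 4.3 times longer than the delay that already triggers removal, on the assumption that a month is 28 to 30 days. The consequence is for patient safety and for consistent discontinuation; no effect on the response-rate conclusion is shown. The protocol gives no Grade 3-4 rash rate for this population. In the adult anti-PD-1 trial described in Section 1.6.3 that lists rash among the common events, most events were low grade, so few patients may be affected.

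**What to change.** Set one disposition per grade and make Sections 6.2, 6.4, 6.4.1 and 7.4 agree.

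- **Grade 4:** permanently discontinue. Split the Grade 3-4 row of Section 6.4.1 so that Grade 4 has no resume step.
- **Grade 3 resolving to Grade 1 or lower within 7 days:** resume at the same dose.
- **Grade 3 beyond 7 days:** remove from protocol therapy, as Sections 6.2 and 7.4 already require. Delete the reinstitution wording from the Grade 3 row of Section 6.4 and the taper-then-resume step from Section 6.4.1.
- **Grade 2 needing systemic steroids:** either remove under Section 6.2 and delete the restart wording in Sections 6.4 and 6.4.1, or exempt skin expressly in Section 6.2.

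If the sponsor does want Chair-approved restart after Grade 3, add that exception to Section 6.2, including its 7-day delay sentence, and to Section 7.4, bounded by the 6-week limit of Section 5.3.

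A sentence stating that Section 6.2 prevails over the organ tables would also help with the pneumonitis overlap, but does not replace these edits.

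The cost is amendment wording and a site memo.

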# 6.4.1 Recommended Skin Adverse Event Management Algorithm

Toxicity	Management	Follow-up
(CTCAE v.4.03)		
Grade 1-2 Rash: Covering ≤ 30% BSA*	
 
Symptomatic therapy (e.g. antihistamines, topical steroids);
 
Continue protocol therapyas per protocol.
 
	
 
If persists >1-2 weeks or recurs:
 
Consider skin biopsy;
 
Hold protocol therapy;
 
Consider 0.5-1.0 mg/kg/day         Methylprednisolone IV or oral         equivalent;
 
Once improving, taper steroids         over at least 1 month;
 
Consider prophylactic antibiotics         for opportunistic infections
 
Then resume nivolumab therapy         per protocol.
 
If worsens:
 
Treat as Grade 3-4.
 

Grade 3-4	Hold or discontinue therapy	If improves to Grade 1:
Rash: Covering	as per protocol'	• Taper steroids over at least 1
> 30% BSA; life	• Consider skin biopsy;	month;
threatening	• Dermatology consult;	Add prophylactic antibiotics for
consequences*^	• 1.0 – 2.0 mg/kg/day	opportunistic infections
	methylprednisolone IV or IV equivalent.	
 
Resume nivolumab therapy as per protocol.
 

Patients on IV steroids may be switched to an equivalent dose of oral corticosteroids (e.g. prednisone) at start of tapering or earlier, once sustained clinical improvement is observed. Lower bioavailability of oral corticosteroids should be considered when switching to the equivalent dose of oral corticosteroids.

'If Stevens-Johnson syndrome (SJS)/ toxic epidermal necrolysis (TEN) is suspected, withhold nivolumab therapy and refer patient for specialized care for assessment and treatment. If SJS or TEN is diagnosed, permanently discontinue nivolumab therapy.

\*Refer o NCI CTCAE v.4.03 for term specific grading criteria.

